NSABP B-06 analyzed 1851 patients with Stage I/II breast cancer randomized to total mastectomy, lumpectomy, or lumpectomy and whole breast irradiation. The breast recurrence rate in lumpectomy alone was 43% in contrast to a 10% breast failure rate for patients receiving lumpectomy and whole breast irradiation.¹³ The EORTC 22881/10882 Trial analyzed 5318 Stage I/II breast cancer patients who underwent lumpectomy with negative margins and axillary lymph node dissection, followed by 50 Gy to the whole breast. They were randomized to receive no boost versus a 16 Gy tumor bed boost. Local recurrence was 7.3% vs. 4.3% at 5 years (no boost versus boost), a 41% reduction in local recurrence.¹⁴ Thus it appears that delivering additional treatment to the tumor bed significantly reduces the chance of local tumor recurrence.

The next question that follows is if the whole breast irradiation can be eliminated altogether with delivery of a high dose of radiation limited only to the site at highest risk for recurrence. By confining treatment to a limited volume of breast tissue adjacent to the lumpectomy cavity, it may allow delivery of higher doses to high risk areas, potentially reducing acute and chronic toxicity, thus improving the quality of life in patients. In addition, the smaller target volumes may allow hypofractionated treatment schedules, which would decrease the time and inconvenience of breast conservation therapy,

eliminate scheduling problems with systemic chemotherapy, and potentially improve outcome by reducing delay to local therapy.

Trials Investigating Partial Breast Irradiation

Investigations of partial breast irradiation have, in fact, been performed, with excellent early results. Primarily Phase I, II and a few Phase III studies have been initiated using: high dose rate (HDR) brachytherapy, low dose rate (LDR) brachytherapy, external beam radiotherapy, and intra-operative radiotherapy.¹⁵⁻³² A hypofractionated treatment scheme has been used in all cases. Local recurrence rate has been <10% in all studies except two, which had poor selection criteria.^{25,26,29} When evaluated, cosmetic results have been rated Good/Excellent in >75% of the patients treated.

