Phase I, II and III studies conducted at the National Institute of Oncology in Hungary have some of the longest follow-up data to date. Forty-five patients with T1 breast cancer were enrolled in the Phase I-II study and underwent lumpectomy followed by HDR brachytherapy 7 x 4.33 Gy or 7 x 5.2 Gy to the tumor bed. With a median follow-up of 57 months, the local recurrence rate was 4.4%. The 5-year probability of cancer-specific, relapse-free and local recurrence-free survival was 90.0%, 85.9%, and 95.6%, respectively. The phase III study was subsequently performed with an additional 126 patients randomized to receive 50 Gy WBRT or HDR brachytherapy 7 x 5.2 Gy to the tumor bed alone. With a median follow-up of 30 months, this study also confirms excellent locoregional tumor control of 100% in both arms. The 3-year probability of cancer-specific and relapse-free survival was essentially equivalent, 98.1% and 98.4% in the WBRT group and 100% and 94.4% in the HDR brachytherapy group.¹⁸

Several institutions have been evaluating accelerated partial breast irradiation using 3D conformal external beam radiotherapy.^{15,29,30} A concern of EBRT is that the breast is a moving target that may require larger volumes of normal breast tissue to be irradiated to avoid a geographic miss. William Beaumont Hospital has been studying this, with careful evaluation of breast motion using standard free-breathing virtual scans compared with CT scans obtained at the end of normal inhalation (NI) and exhalation (NE). They found that 5 mm of margin was sufficient to fully account for breast motion, with minimal use of immobilization devices (alpha cradle). Sixteen patients were treated using a CTV of 1.5 cm plus 1 cm for breathing motion/set-up uncertainty. A dose of 34-38.5 Gy was delivered in 10 fractions BID over 5 days using a 4-5 noncoplanar beam arrangement. With a median follow-up of 8 months, toxicity has been mild, consisting of mild fatigue, mild breast tenderness and mild to moderate erythema/dry desquamation.¹⁵ The RTOG also has a proposed Phase I/II protocol to evaluate 3D CRT confined to the lumpectomy site in Stage I/IIA breast carcinoma.

Rationale for Partial Breast Irradiation with Protons

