2.0 Objectives

- 2.1 To evaluate the technical feasibility of delivering partial breast irradiation with proton beam.
- 2.2 To evaluate the acute and long term toxicity associated with partial breast proton therapy.
- 2.3 To evaluate the cosmetic results with partial breast proton therapy
- 2.4 To determine the local tumor control and survival associated with partial breast proton therapy.

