8.0 Patient Assessments

8.1

Study Parameters

Assessment	Pre TX	1 Mo Post TX	6 MO Post TX then every 6 months	6 MO Post TX then annually
H & P	X	X	X*	
Disease Status	X	X	X*	
Toxicity Assessment	X	X	X*	
Mammo	X			X
CBC & LFT	X	As indicated	As indicated	As indicated
Bone scan or CT scan	As needed	As indicated	As indicated	As indicated
Photos	X			X
Cosmesis Assess. (MD&Pt.)			X	X
Chest X-ray	X			X

* Until year 5 at which time complete assessment will be conducted annually

8.2

Definitions for Cosmetic Outcomes

Cosmetic outcome will be graded by the study subject, radiation oncologist, and surgical oncologist periodically following treatment according to section 8.1. The grading scale will be as follows:

Excellent – the treated breast, when compared to the untreated breast, shows minimal or no changes in shape or size. There may be minimal subcutaneous fibrosis or scarring.

Good – there are mild changes in the size and shape of the treated breast. Scarring within the breast causes mild alterations

in breast shape.

Fair – there is a clear difference in the size and/or shape of the treated breast that involves $\frac{1}{4}$ or less of the treated breast.

Poor – marked changes in the treated breast that involves more than $\frac{1}{4}$ of the breast.

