9.0 Statistics and Data Management

9.1 Initially 25 subjects will be enrolled into this trial. After a toxicity evaluation is completed and felt to be acceptable, 25 additional subjects will be enrolled for a total of 50 subjects.

An additional 50 subjects will be enrolled under the new eligibility criteria defined in the April 4, 2008 revision.

9.2 All acute toxicities will be scored according to the NCI Common Toxicity Criteria v2.0. Late toxicity will be scored per RTOG guidelines. Any toxicities with a threshold of Grade 3 or above will be reported as an adverse event. Frequencies of toxicities will be tabulated and compared to published reports.

9.3 Frequency and type of recurrence (local, regional, distant) will be tabulated and compared to prior studies.

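### Section 9.3 answers objective 2.4 with a recurrence count at an unstated cut-off, which cannot be set fairly against the 3-year and 5-year benchmarks cited, and survival has no planned analysis

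*Combined protocol and SAP*

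**What the plan says.** Section 2.0, objective 2.4, is "To determine the local tumor control and survival associated with partial breast proton therapy". Section 9.3 is the only part of the statistics section that addresses it, in one sentence: "Frequency and type of recurrence (local, regional, distant) will be tabulated and compared to prior studies". Section 9 contains no survival analysis of any kind.

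Section 9.1 enrols in stages. The first 25 subjects are followed by a toxicity evaluation, after which "25 additional subjects will be enrolled for a total of 50 subjects". Then: "An additional 50 subjects will be enrolled under the new eligibility criteria defined in the April 4, 2008 revision". No accrual period, analysis date or minimum follow-up is stated. Section 8.1 schedules disease status every 6 months, with the footnote "Until year 5 at which time complete assessment will be conducted annually". Follow-up therefore continues past 5 years with no stated end.

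Section 9.3 does not say which prior studies it means. Those described in the Introduction are the natural candidates, and their time bases differ:

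- Boost trial (whole breast irradiation without or with a tumor bed boost): local recurrence 7.3% and 4.3% at 5 years.
- Phase I-II brachytherapy study, 45 patients: "The 5-year probability of cancer-specific, relapse-free and local recurrence-free survival was 90.0%, 85.9%, and 95.6%, respectively". A local recurrence rate of 4.4% at a median of 57 months is also given.
- Phase III brachytherapy study: "With a median follow-up of 30 months, this study also confirms excellent locoregional tumor control of 100% in both arms", plus 3-year cancer-specific and relapse-free probabilities.
- Partial-breast studies taken together: local recurrence below 10% in all but two, with no time stated.

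**The concern.** A recurrence frequency (events divided by subjects) rises with the length of follow-up. A 5-year probability does not depend on when the data are cut, apart from its precision. If the first is set beside the second, the difference between them mixes the effect of treatment with the date of the table. Staged enrolment makes this worse, because the later 50 subjects will have had less time to recur than the first 50 at any cut-off.

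Followed as written, section 9.3 could make proton therapy look better than, equal to or worse than a cited 5-year rate for reasons of timing alone. Without an interval, the reader also cannot see how little a handful of events in 50 to 100 subjects can establish. The survival part of objective 2.4 has no pre-specified analysis at all.

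**Working it through.** **The plan's own figures.** Section 9.3 contains no number to reproduce. The cited benchmarks are internally consistent: (7.3 - 4.3)/7.3 = 41.1%, stated as 41%; 2/45 = 4.4% and 43/45 = 95.6%, both as stated (the count of 2 is inferred from 4.4% of 45).

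**Effect of the cut-off.** The inputs are the two cited 5-year rates, F5 = 7.3% and 4.3%. Constant hazard, follow-up spread evenly from a to b years, and no losses are assumptions. The windows are illustrative, since the documents give no accrual dates.

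- Hazard: h = -ln(1 - F5)/5. For 7.3%, h = 0.01516 per year; for 4.3%, h = 0.00879 per year.
- Expected crude frequency: 1 - [exp(-ha) - exp(-hb)] / [h(b - a)].
- Example, 7.3% with 0-4 years: 1 - (1 - exp(-0.0606))/0.0606 = 2.97%.

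| Follow-up (years) | True 5-year rate 7.3% | True 5-year rate 4.3% |
|---|---|---|
| 0-4 | 3.0% | 1.7% |
| 1-5 | 4.4% | 2.6% |
| 1-7 | 5.9% | 3.4% |
| 1-9 | 7.2% | 4.3% |
| 3-7 | 7.3% | 4.3% |
| 5-9 | 10.1% | 6.0% |

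A crude figure near 6% is thus expected from a true 7.3% with 1-7 years of follow-up, and equally from a true 4.3% with 5-9 years. The crude figure matches the 5-year rate only when average follow-up is close to 5 years.

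**Staged entry.** If the first 50 subjects have 4-8 years and the added 50 have 0-4 years, one true rate of 7.3% gives 8.7% in the first group, 3.0% in the second and (8.68 + 2.97)/2 = 5.8% pooled.

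**Precision.** Exact (Clopper-Pearson) 95% intervals: 2/50 = 4.0%, 0.5-13.7%; 4/100 = 4.0%, 1.1-9.9%. Each covers both 4.3% and 7.3%.

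**Kaplan-Meier or cumulative incidence.** With other-cause hazard g = -ln(1 - d)/5, the 5-year cumulative incidence is [h/(h + g)] × [1 - exp(-5(h + g))]. For an assumed 5-year other-cause death d of 5%, 10% or 15%, 7.3% by Kaplan-Meier becomes 7.1%, 6.9% or 6.7%. The choice matters much less than the cut-off.

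**Survival.** No arithmetic is needed. Objective 2.4 names it, and sections 9.1 to 9.4 contain no analysis of it.

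**The case against.** The strongest reply has four parts.

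First, section 9.3 does not exclude a time-to-event method; calling the frequency crude is a reading. That is true, but a tabulated frequency most naturally means a count. A time-to-event analysis would also need an origin, a censoring rule and a time point, none of which is given.

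Second, several cited partial-breast figures are themselves crude or undated, and the 7.3% and 4.3% pair comes from a whole-breast trial. In the phase I-II brachytherapy study, the 4.4% recurrence rate agrees with the 5-year 95.6%. This stands as a limit: the mismatch concerns the 3-year and 5-year figures, not every benchmark. The agreement arises where median follow-up was 57 months, close to 5 years, and nothing in section 9.3 secures the same here.

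Third, the follow-up windows are assumed, and two of them (1-9 and 3-7 years) show almost no error. This also stands. The size of the error is conditional and its direction unknown.

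Fourth, in a small single-arm trial the timing swing is about 3 to 10 events per 100 subjects. The exact intervals for those counts (0.6-8.5% and 4.9-17.6%) both cover 7.3%, and a 5-year estimate would not separate 4.3% from 7.3% either. That limits what any comparison can show. It does not remove a systematic timing error, and it argues for reporting the interval. Nothing elsewhere in the documents fills the gap.

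**Conclusion.** The point holds and should be fixed. Two parts rest on the text alone: section 9.3 fixes no time point, cut-off, estimator, interval or comparator, and survival is a stated objective with no planned analysis. The size of the timing effect rests on the assumptions above. Across plausible windows, a true 5-year rate of 7.3% could be tabulated anywhere from about 3% to 10%, and a true 4.3% from about 2% to 6%. An early table understates 5-year recurrence and a late one can overstate it. No decision rule in the plan depends on the figure, so what is at risk is the fairness of the reported comparison with prior studies.

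**What to change.** Rewrite section 9.3 as follows.

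1. Make the main result the 5-year estimate of local recurrence with a 95% confidence interval, and estimate regional and distant recurrence the same way. State whether this is Kaplan-Meier local control or cumulative incidence with death as a competing event.
2. Add Kaplan-Meier overall survival with a 95% interval, and cancer-specific survival if cause of death is recorded.
3. Define one time origin (for example, first proton treatment). Censor recurrence at the last disease-status assessment and survival at the last date known alive. State the analysis date or minimum follow-up, and report median follow-up and the number at risk at 5 years.
4. Name the prior studies and compare only at matching times (5 years with 5 years, 3 years with 3 years). Use the undated figure of below 10% as context, not as a criterion.
5. Keep the frequency table as supportive, with follow-up shown separately for the first 50 and the added 50 subjects.

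The cost is analysis wording and a check that dates of recurrence and death, and cause of death if used, are captured at visits already scheduled. Section 8.1 lists disease status but does not say that these dates are recorded. No new visits are needed. The one drawback for the sponsor is that, if the analysis is early, the reported recurrence may look less favourable than a raw count.
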